Protocol

1. Project Title:

A Smartphone App to Capture Inhibitory Control as a Novel Moderate Drinking Tool

2. Investigator(s):

[name]. (PI)
[name]. (Co-I)
[name]. (Co-I)
[name]. (Co-I)
[name]., (Collaborator)
[name]. (Consultant)
[name]., MPH (Study Physician)

3. Abstract:

Young adult drinking is a public health issue. Current interventions yield small effect drinking reductions, thus new approaches are needed. Smartphone applications (apps) have great potential for drinking moderation. Almost all young adults own a smartphone and most are open to technology to moderate drinking. There are many drinking apps, but quality varies and there is no evidence any apps are more efficacious than a control condition for young adults. Thus, there is an evidence gap as to which apps may help. Brief interventions have shown that personalized feedback based on motivational interviewing (M.I.) has efficacy, but these interventions give feedback about general patterns only, not drinking and impairment in the moment. Theory and evidence emphasize that slowing pace of drinking is difficult. These findings suggest young adults need more help, preferably while drinking, to slow their pace of alcohol use. Apps have potential for in-the-moment intervention, but there are no efficacious, in-the-moment behavioral interventions for young drinkers. Human laboratory studies support perceived impairment as a focus of an in-the-moment, moderate drinking app. Two studies using different cognitive tasks found heavier drinking young adults underrated impairment more than light drinkers. Simulated driving results in particular suggest serious consequences from misperceived impairment. An app that provides accurate feedback on impairment could increase perceived impairment and reduce drinking. This study will test an app providing in-the-moment feedback on impaired inhibitory control as an adjunct to an existing, M.I.-based, brief web-based intervention that gives feedback on overall drinking. App feedback will be tied to performance on the cued go/no-go task, which tests ability to respond quickly to "go" targets (activation) while withholding responses to "no-go" targets (inhibition). Moderate doses to blood alcohol content (BAC) of .05-.06% reliably lead to inhibition errors, but higher doses are usually needed for "go" reaction time (RT) to slow. Thus, ability to respond remains but ability to inhibit is impaired, which has negative implications. Using M.I. - consonant language, feedback will compare RT and inhibition failures after alcohol to RT and errors pre-drinking, linking performance decrement to consequences like risky sex and driving issues. The experimental app, which will be derived from a larger app in a recent study, will be compared to 2 control conditions in which the task is completed without this novel feedback. Heavy drinking young adults ($N=99$) will be randomized to 1 of the 3 app conditions; attend an individual drinking session and be dosed to $BAC=.06\%$; during which they will use the experimental or a control version of the app. Participants will then attend a group drinking session on a separate day and be dosed to $BAC=.06\%$ in small groups in a bar lab; then use the experimental or a control version of the app, followed by opportunity to self-administer more alcohol. Primary outcomes will be differences between study conditions on BAC and alcohol self-administered. During a 4-week period post-session, all participants will use the experimental app in actual drinking

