 In a pilot study ($N=76$, 67% female, 25% non-white, M age= 43[$SD=14$]), consultant [name] compared a standard CGNG with the app version in his current study, which required 3 min., on average. This app version of the CGNG will be elaborated in the proposed study. Reaction times (RTs) in the app and computer versions were highly correlated ($r=.69$, $p<.01$). The trials in the app version were divided into thirds

[figure not shown]

Figure 2b

and mean RTs were correlated to evaluate reliability. RTs among each third were correlated between .89-.95, indicating strong reliability. Correlations of inhibition errors on the computer version and errors on the app were lower, $r=.28$ ($p=.015$). This is not surprising as CGNG errors are infrequent when sober. This is actually an advantage as it enhances sensitivity to alcohol effects. Given the promising findings and extensive literature on the CGNG⁴⁵⁻⁵¹, we are confident the app version will be sensitive to alcohol. [name] included a description of the app in a preliminary study of young adult drinkers ($N=23$). Participants rated the likelihood they would use the app 5.1 ($SD=1.3$) on a 1-7 scale. In a recent web survey of young adults in FL ($N=72$), [name] found 66% of heavy drinkers reported scores ≥ 3 on a 0-10 scale, indicating agreement they would like to use an app to help reduce drinking, suggesting high interest and a degree of motivation.

Summary: These studies show feasibility; young adults' motivation to use moderate drinking apps even if they take several minutes; our experience with relevant methods; external validity of the CGNG; and reliability and validity of the app version of the CGNG. Thus, the CGNG is a good choice for in-the-moment intervention.

5. Specific Aims

Primary Aim 1: Compare effects of a smartphone app providing feedback on impaired inhibitory control to 2 control conditions on BAC (Aim 1a) and number of alcoholic drinks self-administered (1b) during a 1-hour free drinking period in a naturalistic bar lab that occurs immediately after a fixed alcohol dose targeting BAC= .06%.

Primary Aim 2: In a 4-week period post-session, compare, within-subject, number of drinks per occasion during 2 weeks when participants use the app during actual drinking situations vs. 2 weeks when they will not use the app. Also test app satisfaction including number of times used and likelihood of future use.

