Our goal was to power the study for the Primary and Secondary Aims. Roberts and Fillmore's findings speak to the potential impact of task-based feedback (Preliminary Study 5 [PS5]). Perceived ability to drive post-alcohol declined from $M=46.8(4.7)$ to $29.7(5.5)$ in the higher risk DUI group and only $M=25.8(5.5)$ to $21.2(4.8)$ in the no-DUI group: a large effect difference ($d=1.5$). While not the same as a control condition, the no-DUIs were a subgroup in which the intervention had minimal impact, as with a control condition. Our alcohol study in-progress (Preliminary Study 1 [PS1]) is relevant as a test of effects of an app on alcohol self-administration though the methods are not identical. Since our ongoing study does not begin with a fixed dose targeting a specific BAC, results involving number of alcoholic drinks self-administered are more comparable to the proposed study and more appropriate for power and effect size estimation. In our in-progress study, the smartphone breathalyzer device/app was associated with significantly less alcohol self-administration ($M=3.5$ drinks, $SD=1.3$) than a control condition ($M=4.8$, $SD=1.5$), $d=.89$. Considering these findings, we project a large effect size.

Aim 1 power is based on ability to detect a between-subjects effect of app condition. We used an effect size equivalent to our in-process smartphone breathalyzer study for effect of condition (experimental vs. control groups). This estimated effect is much smaller than in Roberts and Fillmore's prior study providing feedback regarding cognitive impairment to a sample of drinkers with and without a prior DUI. Assuming an effect ($d=.89$) at $\alpha=.025$ (to account for comparisons between the experimental app and each of the other study conditions: standard and control), the proposed sample of 99 completing the lab session and follow-up period yields .90 power. For Primary Aim 2, the goal will be to compare alcohol use in the 2 weeks participants use vs. do

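### Aim 1 has two primary outcomes, but its .025 level covers only the two app contrasts, and the plan does not say how the outcomes jointly decide the aim

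*Combined protocol and SAP*

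**What the plan says.** The Abstract (section 3) states: "Primary outcomes will be differences between study conditions on BAC and alcohol self-administered". Section 5, Primary Aim 1, labels these 1a (BAC) and 1b (number of drinks), each compared between the feedback app and two control conditions.

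The Data analyses part of section 6 defines 1a as peak eBAC, calculated from drinks, elapsed time, weight and sex. It analyses 1a by regression on condition and sex, and says that 1b will be handled in a similar way. It states no significance level for Aim 1 and no rule for combining the two outcomes.

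The Sample, power & effect size part of section 6 gives .90 power for 99 completers at d = .89 and alpha .025. The only reason given for .025 is "to account for comparisons between the experimental app and each of the other study conditions". The effect size comes from the team's ongoing study, on the ground that "results involving number of alcoholic drinks self-administered are more comparable to the proposed study and more appropriate for power and effect size estimation".

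**The concern.** The plan allows for multiplicity within Aim 1 but counts only one of its two sources. Two contrasts on two outcomes make four tests, and .025 is exactly .05/2. With both outcomes called primary and no rule linking them, a significant result on either, for either contrast, could be reported as a positive primary finding. The outcomes also overlap heavily, since 1a is built from 1b, so the second test adds another chance of significance but little new information. At stake is whether a positive Aim 1, meant to support a larger application, carries the error rate that the choice of .025 implies.

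**Working it through.** **Inputs.** From Sample, power & effect size: d = .89, alpha .025, N = 99, 33 per condition. From the Abstract and section 5: two outcomes and two contrasts. From the exclusion criteria: weight 110 to 220 lb. From the group session procedures: starting dose targeting .06%, ceiling .12%. Not in the documents: the correlation rho between 1a and 1b, and whether .025 is one- or two-sided.

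**Step 1. Reproduce the stated power.** The noncentrality is d × √(n/2) = .89 × √(33/2) = 3.615. The two-sided .025 normal critical value is 2.241, so power is Φ(3.615 − 2.241) = Φ(1.374) = .915. The noncentral t with 64 df gives .904. Both agree with the stated .90. One-sided .025 gives .945 (t) or .951 (z) and does not agree, so .025 is read as two-sided.

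**Step 2. Error with one outcome.** The two contrasts share the experimental arm, so with equal arms their test statistics correlate .5. Under the null, P(|Z₁| > 2.241 or |Z₂| > 2.241) = .046. The .025 is therefore adequate for what it was set to cover.

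**Step 3. Error with two outcomes if either counts.** There are four two-sided tests at .025. Correlation is .5 between contrasts, rho between outcomes within a contrast, and .5 × rho otherwise. The upper bounds are 4 × .025 = .10 and, for independent tests, 1 − .975⁴ = .096. Simulation (6 million draws) gives:

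| rho | Aim 1 familywise error |
|---|---|
| 0 | .091 |
| .5 | .085 |
| .7 | .079 |
| .8 | .074 |
| .9 | .066 |
| .95 | .061 |
| .99 | .053 |
| .995 | .051 |
| .999 | .0485 |
| 1 | .046 |

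Simulated t-tests with 33 per arm agree to within about .002. The error falls to .05 only when rho lies between .995 and .999.

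**Step 4. A plausible rho.** A Widmark-type eBAC was built from a .06 start, a .12 ceiling and weights confined to 110-220 lb, with assumed spreads for weight and number of drinks. Adjusted for sex, as in the planned regression, its correlation with drinks was about .88 to .96. That places the error at roughly .06 to .07.

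**Step 5. Error if both outcomes are required for the same contrast.** Simulated familywise error is .012 to .031 for rho from .7 to .95.

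**Step 6. Fixed sequence.** If 1a is tested only after 1b is significant for that contrast, each contrast is held at .025 and Aim 1 at no more than .025 + .025 = .05. Power for 1b is unchanged at .90. If both true effects are d = .89, the chance of claiming 1a is .85 at rho = .7, rising to .88 at rho = .95.

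**The case against.** A reader might infer that Aim 1's error rate is shown to exceed .05. The documents do not support that. The excess depends on letting either outcome count, which the plan does not state, and on testing each outcome at .025, a figure that appears only in the power paragraph. Step 5 shows that requiring both outcomes would remove the excess. Nor do two chances within one contrast break .05: two tests at .025 give .049 at rho = 0 and .033 at rho = .95. The excess appears only when both contrasts and both outcomes are pooled.

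A second tempting reading is an error near .10. That is the bound for unrelated outcomes, and these are closely tied.

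A third is that 1a has no power justification. The plan presents the calculation for the aim as a whole: "Aim 1 power is based on ability to detect a between-subjects effect of app condition". It borrows a standardised effect from drinks because the earlier study is more comparable on that measure, and this does not make drinks the deciding outcome.

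It is also fair to say that the study is preliminary, has one directional hypothesis about self-administered alcohol, and that Exploratory Aim 1 treats peak BAC and drinks as two ways of measuring one quantity. This limits the weight of the point. It does not answer it: both outcomes are labelled primary, the plan itself chose to adjust alpha, and no rule joins the outcomes.

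**Conclusion.** The point holds as a missing decision rule with a modest consequence. If either outcome can carry Aim 1 and each test uses .025, familywise error is about .06 to .07 for rho of .9 to .95, an excess over .05 of about .01 to .02. At rho = .7 it is about .08. With one outcome it is about .046, and with both required it stays below .05. These figures assume 33 per arm, two-sided tests, and a correlation that the documents do not give. Overlap between the outcomes shrinks the excess, but it disappears only above a correlation of about .995. That is implausible when eBAC also depends on time and on body weight that can vary twofold. Whether to adjust across Aims 1 and 2 is a separate choice and is not part of this point.

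**What to change.** In the Data analyses part of section 6, state that each app contrast is tested at two-sided .025 in a fixed sequence: drinks self-administered (1b) first, and peak eBAC (1a) only if 1b is significant for that contrast. Edit the Abstract and Primary Aim 1 to match. Drinks are the natural first test because the d = .89 came from them, but the sponsor could equally put 1a first. What matters is that the order is fixed before analysis.

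The cost is a sentence and two matching edits, with no change in sample size. The outcome tested second can be claimed only after the first: with 1b first, the chance of claiming 1a falls from about .90 to .85-.88 if both true effects are d = .89.

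Other rules would also control the error. Requiring both outcomes for a contrast needs no split, but its success probability is that same .85-.88. A Bonferroni split over four tests (.05/4 = .0125 each) lowers power per test to about .85 at 33 per arm; restoring .90 needs about 38 per arm, or 3 × 38 = 114 in total.
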